Additional efficacy endpoints explored will include accelerometer assessment of gait quantity and quality in real-world activity; z scores on individual tests and summed performance on the cognitive battery, and incident ischemic stroke, transient ischemic attack, hemorrhagic stroke, myocardial infarction, and cardiovascular death. To protect against bias in ascertainment of the recurrent stroke secondary endpoint, analysis to include a) adjudication of potential endpoint stroke events by 2 independent blinded neurologists (preventing rater bias), and b) administration of the Questionnaire to Verify Stroke Free Status at each follow-up visit, to trigger endpoint evaluations (preventing ascertainment bias).

C.14.4. Sample Size Calculations

Subject size is typical sample size for a feasibility study with a device. We are looking at adherence in order to plan a larger phase II/III successor trial.

Sample Size Justification

The primary feasibility and study endpoint is RPreC adherence at 12 months. As we do not expect clinically important differences in adherence among the three groups, it may be possible to combine two or all three groups. In this study, we also wish to test the null hypothesis that the true adherence is at least 75%. The table below gives the lower 90% or 95% confidence bound for 90%, 95% or 100% observed adherence as a function of sample size and the corresponding statistical power for testing the null hypothesis that the true population adherence is 75% versus the one sided alternative of greater than 75%. The current study is not necessarily sufficiently powered for any of the safety or efficacy outcomes. Therefore this is a pilot study in terms of safety and efficacy.

Lower 90% or 95% one sided confidence bound for true adherence

| | adherence=90% | | adherence=95% | | adherence=100% | |
|----|---------------|------------|---------------|------------|----------------|----------------|
| | 90% | 95% | 90% | 95% | | |
| Ν | confidence | confidence | confidence | confidence | 90% confidence | 95% confidence |
| 20 | 75.5% | 71.8% | 81.9% | 78.5% | 89.1% | 86.1% |
| 40 | 81.0% | 78.5% | 87.2% | 85.1% | 94.4% | 92.8% |
| 60 | 83.1% | 81.2% | 89.2% | 87.6% | 96.2% | 95.1% |

Power for one sided test against null hypothesis of 75% vs > 75%

| | adherence=90% | | adherence=95% | | adherence=100% | |
|----|---------------|------------|---------------|------------|----------------|------------|
| Ν | alpha=0.10 | alpha=0.05 | alpha=0.10 | alpha=0.05 | alpha=0.10 | alpha=0.05 |
| 20 | 0.677 | 0.392 | 0.925 | 0.736 | >0.99 | >0.99 |
| 40 | 0.901 | 0.794 | 0.997 | 0.986 | >0.99 | >0.99 |
| 60 | 0.966 | 0.927 | 1.000 | 0.999 | >0.99 | >0.99 |

C.15. Risk Assessment

C.15.1. Formal risk analysis with regard to anticipated risk associated with the device is provided below as per IDE 130167. Risks have been minimized or eliminated through appropriate design control and preclinical testing and bench testing of the device.

The risks associated with the autoRIC are consistent with those of a standard automatic blood pressure cuff, including local bruising, abrasion, and pain at the site of the cuff. Although extremely unlikely to occur, in the case of a serious device failure, hypothetical harms to the patient could include nerve or bone damage.

As presented in Section 1.5 (IDE 130167), previous investigations have reported minimal to no safety implications associated with RIC. In clinical studies where the benefit of RIC was not statistically significant there was no compromise to patient safety. Although the RIC protocol was performed manually in the investigations reported in the literature review, the autoRIC was verified to meet the applicable requirements of standard automated blood pressure cuffs and the performance validation testing conducted on the autoRIC ensures that it performs as intended. As

such, the same performance results can be expected when the RIC protocol is automated by the autoRIC.

C.15.2. Risks associated with MRI:

The MRI scanner does not involve harmful ionizing radiation and is generally well-tolerated. There are no known harmful side-effects associated with temporary exposure to the strong magnetic field used by MRI scanners. There are no known long term risks or complications of MRI. However, there are important safety concerns to consider before performing or undergoing an MRI scan:

- 1. The magnet may cause pacemakers, artificial limbs, and other implanted medical devices that contain metal to malfunction or heat up during the exam.
- 2. Any loose metal object may cause damage or injury if it gets pulled toward the magnet.
- 3. Dyes from tattoos or tattooed eyeliner can cause skin or eye irritation.
- 4. Medication patches can cause a skin burn.
- 5. The wire leads used to monitor an electrocardiogram (ECG) trace or respiration during a scan must be placed carefully to avoid causing a skin burn.
- 6. Prolonged exposure to radio waves during the scan could lead to slight warming of the body.

C.15.3. Other anticipated risks:

Possible complications may occur during the procedure. The complications include but are not limited to, deep venous thrombosis or lymphatic occlusion, petechiae development, skin rash or sensitivity to the cuff, claustrophobia or nerve, bone, or muscle injury. As such, the risk mitigation policy will include, but is not limited to, periodic visual inspection of skin in arms, motor and sensory examinations of the hand to be performed at all office visits.

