During periods of active treatment, RPreC will be induced twice a day by using the autoRIC[™] device (which delivers four remote ischemic conditioning cycles of five minute intervals followed by five-minutes of normal blood flow) around both upper body extremities. The RPreC intervention will be add-on therapy to guideline-based best standard medical prevention therapy. The study will have a randomized phase and a follow-up phase. 60 enrolled patients will be randomized 2:1 to best standard medical care plus active RPreC for 1 year and then follow-up for 1 year versus best standard medical care alone for 1 year and then active RPreC for 1 year. Primary outcome measures will be obtained at the end of the first randomized year (staggered start RCT design). Successful completion of this trial will delineate the feasibility and safety, and explore biomarker indicators of potential efficacy, of inducing brain ischemic tolerance in small vessel stroke-prone patients.

A.1. Specific Aim 1: Feasibility

To establish the feasibility of remote ischemic preconditioning as a sustained therapy for prevention of ischemic brain injury from cerebral small vessel disease.

This aim will be accomplished by demonstrating the remote ischemic preconditioning treatment can be successfully implemented with more than 75% adherence among enrolled patients throughout the 1-year of active treatment. Both patient self-report and remote physiologic monitoring will be performed to quantify patient behavioral adherence to the treatment regimen, and remote physiologic monitoring will be used to quantify physiologic attainment of brief ischemia states in the upper extremities. Establishment of feasibility will allow for subsequent larger, definitive clinical trials of RPreC as a treatment to confer long-term protection against ischemic brain injury due to cerebral small vessel disease.

A.2. Specific Aim 2: Safety

To determine the safety of remote ischemic preconditioning as a sustained therapy for prevention of ischemic brain injury from cerebral small vessel disease.

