This is a single site, feasibility, randomized, dose-ranging clinical trial of remote ischemic preconditioning. During periods of active treatment, induced twice a day by using the autoRICTM device around both upper body extremities which would deliver four remote ischemic conditioning cycles of five minute intervals followed by five-minutes of normal blood flow. The RPreC intervention will be add-on therapy to guideline-based best standard medical prevention therapy. The study will have a randomized phase and a follow-up phase. 60 enrolled patients will be randomized 1:1:1 to 1 year of best standard medical care alone, best standard medical plus active once-daily RPreC, or best standard therapy plus active twice-daily RPreC. Following the 1 year randomized phase, the medical control group will cross over to once (10 patients) and twice (10 patients) daily RPreC for 1 additional year (staggered start design, allowing for collection of additional feasibility and safety data and control group adherence to follow-up). Primary outcome measures will be obtained at the end of the first randomized year.

C.2. Technology

Remote Ischemic Preconditioning Device: The autoRICTM device is a new, portable, automated conditioning device, designed and developed by CellAegis Devices Inc., Canada. The device consists of a Control Unit, Charging Cradle, a Power Adaptor, a Wall Mount for the charging cradle (with wall plug and screws) and Applicator Cuffs. The control unit is a stand-alone reusable controller that controls the inflation and deflation cycles of the Applicator Cuff. The Control Unit clicks into the disposable Applicator Cuff when it is ready for use. The Applicator Cuff is a single-used, disposable cuff that is fastened using Velcro into which a 'one button' battery-driven actuator system inserts. This provides for a mobile 'point-of-care' delivery of RIC that will not impose on other care delivery, and requires no special expertise for its use. The active device is programmed to inflate the cuff to 200 mmHg for five (5) minutes (ischemia) then be deflated for five (5) minutes (reperfusion) completing one cycle of ischemia-reperfusion; the RIC therapy cycle consists of a total of four (4) cycles of ischemia-reperfusion, which the autoRIC Device is programmed to automatically deliver.

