In this study, the device will be used with Applicator Cuffs bilaterally for 12 months to provide ischemic preconditioning therapy to the patient's upper extremities. The applicator cuffs are available in three different adult sizes according to the SP10 standard (small, medium or large) and the cuff is selected to match the arm size of the patient. To assure a total cessation of blood flow

through the limb during the ischemic duration, the cuff inflation pressure is maintained at 200 mm Hg. By Doppler ultrasound, it has been documented that inflation of the blood pressure cuff to 200mm Hg causes cessation of blood flow in the arm^{1,2}. A total of four (4) inflation and deflation cycles will be applied in five (5) minute intervals twice a day. At the end of this automated process, the Procedure Complete indicator is illuminated and an audible tone is heard. The autoRICTM will be used for 12 months to deliver remote ischemic conditioning to the patient. There have been no reported experiences of any side effects in preclinical and clinical studies.

In addition to the autoRIC® Device, CellAegis Devices, Inc. developed the CRICtrac[™] Mobile Application that allows the clinician and coordinators to monitor compliance of each individual study participant. Once the patient has been assigned to a treatment group, the coordinator will initialize new patient cuffs by scanning them using the CRICtrac[™] Mobile App on a compatible Android smartphone equipped with a near-field antenna utilizing a Wi-Fi network connection. During the course of the trial or at the end of the trial, patient compliance can be monitored using the CRICtrac[™] Data Portal providing that the cuff has been scanned. The compliance data is immediately uploaded to the CRICtrac[™] Data Portal. The Data Portal can then be accessed via a link from the Mobile App or on any device with internet access. Once logged in, Trial Coordinators can view and/or export patient and trial information.

C2.1. Device Training

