- 14. Pre-existing neurologic, psychiatric, or advanced systemic disease that would confound the neurological or functional outcome evaluations
- 15. SBP <90 or > 200
- 16. Known history of limb vascular disease, limb vascular bypass surgery, or limb deep venous thrombosis
- 17. All women status post mastectomy (standard-of-care re: blood pressure proscription ipsilateral to prior mastectomy)
- 18. Patients with a contraindication to taking blood pressure in the arm for any reason;
- 19. Patients with a known bleeding disorder or known abnormality of blood flow to the limb.
- 20. Patients with osteoporosis or other bone disorders
- 21. Patients with peripheral nerve injury
- 22. Patients with abnormal nerve supply
- 23. Patients with peripheral neuropathy
- 24. Patients with pre-existing traumatic injury to the limb.
- 25. Prisoners
- 26. Homeless individuals
- 27. Patient unable to give informed consent and no available legally authorized representative to provide informed consent
- 28. Patient unlikely to be compliant with therapy/ unwilling to return for follow up visits
- 29. Concurrent participation in another study with investigational drug or device treatment
- 30. Other likely specific cause of stroke (e.g. dissection, vasculitis, prothrombotic diathesis, drug abuse)

C.4. Enrollment and Consent

After initial patient contact and assessment, the physician-investigator will review the patient's relevant medical history and will verify the diagnosis of small subcortical stroke and moderate to severe WMH and determine eligibility for study entry according to inclusion and exclusion criteria above. Study participants who are competent or who have a legally authorized representative will be enrolled.

C.6. Study Treatment

Randomized Phase: Following signing of the consent form, the patient will be randomized and depending on randomization receive treatment with RPreC once daily, twice daily, or none for 1 year. The RPreC procedure will consist of up to four 5-minute cycles of bilateral upper extremity ischemia, separated by 5-minute periods of reperfusion. Primary outcome measures will be obtained at 1 year.

Follow-up Phase: Patients assigned to RPreC in the first year will exit the trial at the end of Year 1. In contrast, patients assigned to the control arm in the first year will at the start of Year 2 enter a staggered therapy start phase, receiving active RPreC for 1 year (randomized 10 to once daily

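### Once-daily and twice-daily arms are randomised, yet three sentences prescribe twice-daily treatment for all, and the 75% feasibility rule is tied to neither regimen, so a pooled point result could pass with one regimen well below 75%

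*Combined protocol and SAP*

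**What the plan says.** **Allocation.** C.1 describes the study thus: "This is a single site, feasibility, randomized, dose-ranging clinical trial of remote ischemic preconditioning". It then states that "60 enrolled patients will be randomized 1:1:1 to 1 year of best standard medical care alone, best standard medical plus active once-daily RPreC", with twice-daily RPreC as the third arm. C.6 agrees: depending on randomisation, patients "receive treatment with RPreC once daily, twice daily, or none for 1 year". After Year 1, "the medical control group will cross over to once (10 patients) and twice (10 patients) daily RPreC for 1 additional year", and C.6 repeats that split, with controls "receiving active RPreC for 1 year (randomized 10 to once daily" and the other 10 to twice daily.

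**Frequency.** Three sentences do not distinguish the arms:
- Section A: "During periods of active treatment, RPreC will be induced twice a day by using" the device.
- The opening of C.1, in the same paragraph as the 1:1:1 allocation: "During periods of active treatment, induced twice a day by using" the device.
- C.2: "A total of four (4) inflation and deflation cycles will be applied in five (5) minute intervals twice a day".

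**Feasibility criterion.** C.14.3 counts the procedure as feasible if the targets are met in at least 75% of cases. Aim 1 (A.1) asks for adherence strictly above 75% among enrolled patients. Neither names a regimen. C.14.4 adds a one-sided test of 75% against a higher value, tabulated for N = 20, 40 and 60. It says that groups might be combined because no important adherence difference is expected. It gives no basis for that expectation and no criterion for combining.

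**The concern.** Adherence at 12 months is the primary endpoint, and C.14.4 says that it is wanted for planning a larger successor trial. A trial that randomises to two frequencies should be able to say which of them patients sustain. Twice daily asks for double the number of sessions, so equal adherence is a hypothesis and not a given. If only a pooled percentage is judged, a well-kept once-daily arm can carry a poorly kept twice-daily arm (or the reverse) over the threshold, and the next trial could take forward the wrong schedule.

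The twice-a-day sentences add to this. Prescribed frequency is the natural denominator of adherence, and the protocol states two frequencies for the once-daily arm without saying which one counts.

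**Working it through.** **1. Is the allocation itself in doubt?** No. C.1, C.6 and the Year 2 split all describe once-daily and twice-daily groups. The 2:1 ratio in A and C.3 (40 active, 20 control) equals 1:1:1 with the two device arms counted together: 20 + 20 = 40. Only the three frequency sentences are out of line.

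**2. The plan's own power figures.** Inputs from C.14.4: null 75%, one-sided, true adherence 90%. The critical value r is the smallest count with P(X ≥ r | n, 0.75) ≤ alpha, and power is P(X ≥ r | n, 0.90).

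| n | alpha | r | P(X ≥ r) at 75% | Power at 90% | Plan |
|---|---|---|---|---|---|
| 20 | 0.10 | 18 | 0.0913 | 0.6769 | 0.677 |
| 20 | 0.05 | 19 | 0.0243 | 0.3917 | 0.392 |
| 40 | 0.10 | 34 | 0.0962 | 0.9005 | 0.901 |
| 40 | 0.05 | 35 | 0.0433 | 0.7937 | 0.794 |

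All agree within 0.001. The table is sound.

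**3. What can a pooled pass conceal?** Take a case to be a patient, with 20 per regimen. An arm is below 75% if it has 14/20 or fewer.

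| Reading of 75% | Pooled count needed | Splits at that count with an arm below 75% |
|---|---|---|
| At least 75% (C.14.3) | 30/40 | 16+14, 17+13, 18+12, 19+11, 20+10 |
| Above 75% (A.1) | 31/40 | 17+14, 18+13, 19+12, 20+11 |
| Test, alpha 0.10 | 34/40 | 20+14 only |
| Test, alpha 0.05 | 35/40 | none, since 35 − 20 = 15 |

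Under the C.14.3 point rule one regimen can be as low as 10/20 = 50%.

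**4. How likely is that?** The documents give no adherence by frequency, so this is an assumption with a range: true adherence 90–95% once daily and 60–70% twice daily. Let X and Y be independent binomial counts out of 20. The probability is the sum of P(X=x)·P(Y=y) over x+y ≥ threshold and y ≤ 14.

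| Threshold | Probability over the range |
|---|---|
| 30/40 | 0.43–0.61 |
| 31/40 | 0.31–0.50 |
| 34/40 | 0.015–0.069 |
| 35/40 | 0 |

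A twice-daily result as low as 11/20 together with a pooled 30/40 or more has probability 0.03–0.16 over the same range. With a smaller assumed gap (80% and 70%), the chance that the pool reaches 30/40 with at least one arm below 15/20 is 0.25.

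**5. Would a pass/fail rule for each regimen be better?** Not clearly. P(X ≥ 15 of 20) is 0.989 at true 90%, so two such regimens both pass with probability 0.989² = 0.978. At true 80%, which is still above target, it is 0.804, so both pass with probability 0.804² = 0.647, against 0.839 for the pooled 30/40. In the other direction, a regimen truly at 60–70% reaches 15/20 in 13–42% of trials. Precision is also poor: at 15/20 the exact one-sided lower bounds are 58.5% (90% confidence) and 54.4% (95%).

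**The case against.** The best defence is that analysis by arm is already the natural reading. C.11 places the primary endpoint in the intervention arms, in the plural. C.14.4 makes combining conditional and tabulates N = 20. Where the protocol wants pooling, as in the DSMB rule in C.14.1, it says so. C.14.3 calls the primary endpoints descriptive, so 75% is not a confirmatory gate. Figure 5, which is not in the available text, may show the arms. All this makes by-arm reporting plausible, but none of it is a commitment, and a figure would not correct the three sentences.

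A reader might infer three stronger things.

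- **That the frequency conflict corrupts the primary result.** If adherence is completed over prescribed sessions (an assumption; the plan gives no formula), a perfect once-daily patient scored against twice daily would get 365/730 = 50%. No section prescribes that scoring. A.1 measures adherence to the treatment regimen, and C.6 sets the regimen by randomisation. The sentences look like leftover wording.
- **That 43–61% is the trial's expected risk of a concealed failure.** It needs both a governing point threshold and a true gap of 20–35 points. The documents support no such gap, and C.14.4 expects none.
- **That each regimen must pass its own 75% verdict.** Step 5 shows that this is a trade-off at n = 20: about 35% of trials with both regimens truly at 80% would fail at least one.

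**Conclusion.** The point holds in a limited form. Three sentences contradict the once-daily arm and need correcting. Separately, the feasibility rule is tied to no regimen and pooling is left open, so under the C.14.3 point rule 30/40 could be declared feasible with one regimen at 55%, or at the extreme 50%. Under the pooled one-sided test the gap is nearly closed at alpha 0.10 (one split only) and fully closed at 0.05. The split counts assume only that a case is a patient and that the arms hold 20 each; the probabilities also depend on the assumed adherence rates. There is no error in the allocation or the power table. It should be fixed because it touches the primary endpoint and the remedy is almost free.

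**What to change.** 1. In A, the opening of C.1 and C.2, replace the twice-a-day wording with: once or twice a day according to randomised arm.
2. Define adherence against the frequency assigned at randomisation.
3. In C.14.3, commit to reporting adherence for each randomised regimen (n=20, with a one-sided confidence bound) beside the pooled 40-patient figure. State that a regimen will not be described as feasible on the pooled result alone when its own observed adherence is below 75%.
4. Keep the formal test on the pooled 40, and label the per-regimen figures descriptive and imprecise. A mandatory pass/fail verdict per regimen is not required.

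**Cost.** Edits to four sections and a few table rows. No further patients or data are needed, since C.2 has compliance captured per participant and exportable. The price is imprecision: the plan's own lower bounds for 90% observed adherence at N=20 are 75.5% (90% confidence) and 71.8% (95%). Keeping the test pooled preserves power of 0.901 or 0.794 (alpha 0.10 or 0.05, true adherence 90%), against 0.677 or 0.392 in a single arm.
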